5.3 Exclusion criteria

Patients eligible for this study must not meet **any** of the following criteria:

1. Symptomatic or uncontrolled brain metastases requiring concurrent treatment, inclusive of but not limited to surgery, radiation and/or corticosteroids.
2. History of another primary malignancy except for:
 - Malignancy treated with curative intent and with no known active disease ≥ 2 years before the first dose of study drug and of low potential risk for recurrence
 - Adequately treated non-melanoma skin cancer or lentigo maligna without evidence of disease
 - Adequately treated carcinoma in situ without evidence of disease
3. Active or prior documented autoimmune disease within the past 2 years
NOTE: Patients with vitiligo, Grave's disease, or psoriasis not requiring systemic treatment (within the past 2 years) are not excluded.
4. Active or prior documented inflammatory bowel disease (e.g., Crohn's disease, ulcerative colitis)
5. History of interstitial lung disease or non-infectious pneumonitis
6. History of primary immunodeficiency
7. History of allogeneic organ or stem cell transplant
8. Ongoing or prior treatment with A2aR inhibitors. Patients previously treated with A2aR inhibitors for non-oncologic indications (e.g. Parkinson's disease) may be considered for enrollment on a case by case basis.
9. More than 2 or 3 prior lines of therapy (as indicated for each tumor type in the inclusion criteria 4), except for Japanese safety run-in part and DLBCL patients.
10. Systemic anti-cancer therapy within 2 weeks of the first dose of study treatment.
For cytotoxic agents that have major delayed toxicity, e.g. mitomycin C and nitrosoureas, 6 weeks is indicated as washout period. For patients receiving anticancer immunotherapies, 4 weeks is indicated as the washout period. GnRH therapy to maintain effective testosterone suppression levels is allowed for mCRPC patients.

11. Non-palliative radiotherapy within 2 weeks prior to the first dose of study drug. Palliative radiotherapy to a limited field, such as for the treatment of bone pain or a focally painful tumor mass is allowed. To allow for assessment of response to treatment, patients must have remaining measurable disease that has not been irradiated.
12. Major surgery within 2 weeks of the first dose of study treatment (mediastinoscopy, insertion of a central venous access device, and insertion of a feeding tube are not considered major surgery).
13. Current or prior use of immunosuppressive medication within 28 days before the first dose of PDR001, with the exception of intranasal/inhaled corticosteroids or systemic corticosteroids at physiological doses (not exceeding equivalent of 10 mg/day of prednisone)
14. Any of the following clinical laboratory results during screening (i.e., within 21 days before the first dose of study treatment):
 - Absolute Neutrophil Count $<1.0 \times 10^9/L$
 - Platelets $<100 \times 10^9/L$ (for DLBCL patients platelets $< 75 \times 10^9/L$)
 - Hemoglobin (Hgb) $<9 \text{ g/dL}$ (for DLBCL patients Hgb $< 8\text{g/dL}$)
 - Serum creatinine $>1.5 \text{ mg/dL}$ OR Creatinine Clearance $< 45 \text{ mL/min}$ using Cockcroft-Gault formula ([Appendix 6](#))
 - Total bilirubin $>1.5 \times$ Upper limit of normal (ULN)
 - Aspartate transaminase (AST) $> 3 \times$ ULN
 - Alanine transaminase (ALT) $> 3 \times$ ULN
15. Mean QT interval corrected for heart rate (QTcF) $\geq 470 \text{ ms}$ calculated from 3 electrocardiograms (ECGs – in triplicate ≥ 1 minute apart)
16. Any unresolved toxicity ($>$ Common Terminology Criteria for Adverse Events (CTCAE) grade 2) from previous anti-cancer therapy. Patients with irreversible toxicity that is not reasonably expected to be exacerbated by the investigational product may be included (e.g., hearing loss, peripherally neuropathy)
17. History of severe hypersensitivity to any ingredients of study drug(s) and other monoclonal antibodies and/or their excipients. Patients previously exposed to anti-PD-1/PD-L1 treatment who are adequately treated for skin rash or with replacement therapy. Changes to the protocol for endocrinopathies should not be excluded
18. Uncontrolled concurrent illness including, but not limited to, ongoing or active infection, symptomatic congestive heart failure, uncontrolled hypertension, unstable angina pectoris, cardiac arrhythmia, active peptic ulcer disease or gastritis, active bleeding diatheses including any subject known to have evidence of acute or chronic hepatitis B, hepatitis C or human immunodeficiency virus (HIV), or psychiatric illness/social situations that in the investigator's opinion would limit compliance with study requirements or compromise the ability of the subject to give written informed consent
19. Known history of previous clinical diagnosis of tuberculosis
20. History of leptomeningeal carcinomatosis
21. Receipt of any live vaccine within 4 weeks prior to study entry or within 4 weeks of receiving PDR001 or NIR178

22. Pregnant or nursing (lactating) women
23. Any condition that, in the opinion of the investigator, would interfere with evaluation of study treatment or interpretation of patient safety or study results
24. Smoking (e.g. cigarettes, cigars and pipe) must be discontinued at least 7 days prior to initiating study drug administration; smoking cessation products (e.g. transdermal nicotine patches or chewing gum) may be used.
25. Concurrent administration of strong inhibitors or moderate inducers of CYP1A2 is not permitted; administration must be discontinued at least 7 days prior to initiating study drug administration
26. Concurrent administration of sensitive and narrow therapeutic index substrates of CYP1A2 is not permitted; administration must be discontinued at least 7 days prior to initiating study drug administration
27. History of severe hypersensitivity reactions, which in the opinion of the investigator may pose an increased risk of serious infusion reaction.
28. Use of hematopoietic colony-stimulating growth factors (e.g. G-CSF, GM-CSF, M-CSF), thrombopoietin mimetics or erythroid stimulating agents ≤ 2 weeks prior to start of study treatment. If erythroid stimulating agents were initiated more than 2 weeks prior to the first dose of study treatment and the patient is on a stable dose, they can be maintained.
29. History or current diagnosis of cardiac disease indicating significant risk of safety for patients participating in the study such as uncontrolled or significant cardiac disease, including any of the following:
 - recent myocardial infarction (within last 6 months),
 - uncontrolled congestive heart failure,
 - unstable angina (within last 6 months),
 - clinically significant (symptomatic) cardiac arrhythmias (e.g., sustained ventricular tachycardia, and clinically significant second or third degree AV block without a pacemaker).
30. Specific underlying conditions for oral agents. For example: impairment of gastrointestinal (GI) function or GI disease that may significantly alter the absorption of oral NIR178 (e.g., ulcerative diseases, uncontrolled nausea, vomiting, diarrhea, malabsorption syndrome, small bowel resection or presence of more than or equal to Grade 2 toxicity (except alopecia) due to prior therapy)
31. Women of child-bearing potential, defined as all women physiologically capable of becoming pregnant, **unless** they are using highly effective methods of contraception during dosing and for 150 days after the last dose of PDR001 or 30 days after the last dose of NIR178, whichever occurs later. Highly effective contraception methods include:
 - Total abstinence (when this is in line with the preferred and usual lifestyle of the subject. Periodic abstinence (e.g., calendar, ovulation, symptothermal, post-ovulation methods) and withdrawal are not acceptable methods of contraception
 - Female sterilization (have had surgical bilateral oophorectomy with or without hysterectomy), total hysterectomy, or tubal ligation at least six weeks before taking study treatment. In case of oophorectomy alone, only when the reproductive status of the woman has been confirmed by follow up hormone level assessment

- Male sterilization (at least 6 months prior to screening). The vasectomized male partner should be the sole partner for that subject
- Use of oral, injected or implanted hormonal methods of contraception or placement of an intrauterine device (IUD) or intrauterine system (IUS), or other forms of hormonal contraception that have comparable efficacy (failure rate <1%), for example hormone vaginal ring or transdermal hormone contraception.

In case of use of oral contraception women should have been stable on the same pill for a minimum of 3 months before taking study treatment.

Women are considered post-menopausal and not of child bearing potential if they have had 12 months of natural (spontaneous) amenorrhea with an appropriate clinical profile (e.g. age appropriate [generally age from 40 to 59 years], history of vasomotor symptoms [e.g. hot flush]) in the absence of other medical justification or have had surgical bilateral oophorectomy (with or without hysterectomy), total hysterectomy, or tubal ligation at least six weeks ago. In the case of oophorectomy alone, only when the reproductive status of the woman has been confirmed by follow up hormone level assessment is she considered not of child bearing potential.

32. Sexually active males unless they use a condom during intercourse while taking drug and 30 days after stopping NIR178. Sexually active males should not father a child in this period.

6 Treatment

6.1 Study treatment

[figure not shown]
For this study, the investigational drugs are NIR178 and PDR001. The study treatment is defined as NIR178 in combination with PDR001. Please note that additional dosage strengths for any of the study drugs may become available. They will be given as the following dose strength and forms:

Table 6-1 Dose and treatment schedule

Study treatments	Pharmaceutical form and route of administration	Dose	Frequency and/or Regimen		
			Part 1	Part 2	Part 3
NIR178	40mg, 80mg and/or 160mg capsules for oral use	160mg, 240mg*	Continuous BID	Continuous and intermittent BID per randomization	Continuous or intermittent BID based on Part 1 and Part 2 results
NIR178**	80mg, 240mg Film-coated tablet for oral use	160mg 240mg	Not applicable	Not applicable	Continuous BID
PDR001	100mg powder for solution for infusion	400mg	Every 4 weeks		

*All newly enrolled patients under Amendment 5 will receive NIR178 240mg BID

**As of Protocol Amendment 6, patients enrolled in Part 3 will receive continuous dosing of NIR178 FCT in combination with PDR001

NIR178

NIR178 will be administered at 160 mg orally twice daily (BID) either continuously or based on the assigned intermittent dosing schedule. As of Amendment 5, all newly enrolled patients will be treated with NIR178 240mg BID. As of amendment 6, in Part 3 of the study, NIR178 FCT will be administered orally twice daily (BID) on a continuous dosing schedule starting with a dose of 160 mg BID, that may be increased to 240 mg BID based on safety and pharmacokinetic data available after the initial 10 patients are treated.

Patients should take NIR178 twice daily at approximately the same time each day in the morning and evening and should ensure there is an approximate 12-hour interval between each daily dose. On days that PK samples are obtained, the patient should take NIR178 during the clinic visit after the pre-dose PK samples and prior to post-dose PK samples, when instructed by the study staff. The patient should not take the morning dose of NIR178 at home during inpatient visits, particularly in those with PK assessments.

Patients should take NIR178 on an empty stomach (i.e. fast from food and drink, except water) at least 1 hour before or 2 hours after a meal. Each dose may be taken with a glass of water (approximately 8 ounces or approx. 235 mL). An ongoing clinical study (CNIR178X2103J) in NSCLC patients includes an investigation of the impact of food on NIR178 PK. If the results of this study indicate that NIR178 may be taken with or without regard to food, the fasting requirement may be removed and administration instructions will be communicated in writing by Novartis.

Patients should be instructed to swallow whole capsules or tablets and not to chew or open them.

If vomiting occurs during the course of treatment, patients should not take the study drug (NIR178) again before the next scheduled dose.

Patients should be instructed not to make up missed doses. A missed dose is defined as a case when the full dose is not taken within 4 hours after the approximate time of the usual daily dosing. That day's dose should be omitted and the patient should continue treatment with the next scheduled dose.

PDR001

PDR001 will be administered via IV infusion over 30 minutes once every 4 weeks. Infusions of PDR001 can be extended to up to 2 hours if clinically indicated.

Further instructions for the preparation and dispensation of NIR178 and PDR001 are described in the CNIR178X2201 Pharmacy Manual.

Both study drugs will be administered on the same day. The first doses of the combination of NIR178 and PDR001 are administered at Cycle 1 Day 1, which defines the patient's treatment cycles for the study. The start time of PDR001 infusion on dosing days can occur at any given time regardless of the dose administration schedule of NIR178.

All dosages prescribed and dispensed to patients and all dose changes during the study must be recorded on the Dosage Administration Record eCRF.

Dose modifications and reductions should be followed described in [Section 6.2.1](#) and [Section 6.2.2](#).

6.1.1 Dosing regimen

Treatment cycle is defined as 28 days.

In Part 1 of the study, all patients will receive NIR178 240 mg twice daily continuously and 400 mg of PDR001 administered every 28 days (prior to Amendment 5, all patients were treated with NIR178 160 mg BID).

In Part 2 of the study, all patients will be randomly assigned to one of the three NIR178 dosing schedules in combination with PDR001:

1. NIR178 S1: Patients will take NIR178 160mg twice daily continuously with PDR001 400mg administered once on day 1, every 28 days.
2. NIR178 S2: Patients will take NIR178 160mg twice daily on days 1-14 of a 28 day cycle together with PDR001 400mg administered once on day 1 every 28 days.
3. NIR178 S3: Patients will take NIR178 160mg twice daily on days 1-7 and days 15-21 of a 28 day cycle together with PDR001 400mg administered once on day 1 every 28 days.

In Part 3 of the study, one or two tumor groups may be selected based on emerging data from Part 1 and Part 2.

As of protocol amendment 6, Part 3 will be opened in parallel with Part 1 to further assess TNBC patients with a PD-L1 SP-142 status of IC=0 (<1%) using NIR178 FCT formulation continuous dosing schedule in combination with PDR001. A second tumor group may be considered for Part 3 after completion of Part 1. The first 10 patients enrolled in Part 3 will receive a NIR178 dose of 160 mg BID FCT, and after all patients complete at least 1 cycle of treatment, safety and PK analysis will be performed to decide whether the dose should be increased to NIR178 240 mg BID FCT. If there is unexpected toxicity due to formulation change the dose will not be escalated to NIR178 240mg BID FCT and an additional 10 patients will be enrolled at NIR178 160mg BID FCT. If the NIR178 160mg BID FCT formulation is considered safe, dose escalation to NIR178 240 mg BID FCT will occur and an additional 20 patients will be enrolled.

In the Japanese safety run-in part, patients will take NIR178 at 80 or 160mg twice daily continuously during the Cycle 1, and then starting from Cycle 2D1, will receive NIR178 twice daily continuously in combination with PDR001 400mg administered once on day 1 every 28 days. The starting dose of NIR178 80mg is 50% of the RoW starting dose at which no DLT was observed in the CNIR178X2103J phase I/Ib study in combination with PDR001. As of protocol amendment 6, patients enrolled in the Japanese safety run-in part will receive NIR178 240mg twice daily in combination with PDR001 400 mg administered on day 1 of every 28 day cycles.

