In the ongoing CNIR178X2201 trial, as of August 3, 2020, 13 patients were treated with the NIR178 240mg dose in combination with PDR001 400mg Q4W with available safety data. The first 10 patients enrolled at the NIR178 240mg dose, have completed at least one cycle of treatment with G3 AEs suspected to be related to study drug occurring in two patients. Less than 33% of the first 10 patients enrolled in this regimen experienced a G3/G4 AE suspected to be related to study drug, which is below the defined threshold as outlined in [Section 6.2.3](#). To date, the dose of NIR178 240mg BID in combination with PDR001 400mg Q4W has shown to be safe and well tolerated.

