2.3 Rationale for dose and regimen selection

[figure not shown]
In this study the selection of dosing regimen is based on the currently available preclinical and clinical safety, efficacy, PK and PK/PD information for the NIR178 and PDR001 combination. Based on currently available data from the ongoing phase 1b study (CNIR178X2103J), NIR178 160mg BID will be administered (continuous or intermittent dosing schedule) in combination with PDR001 at 400 mg every 4 weeks in this phase II study. All newly enrolled patients under Amendment 5 will receive NIR178 240 mg BID in combination with PDR001 400 mg every 4 weeks. Patients enrolled in Part 3 of the study will receive the new FCT formulation of NIR178, starting with a dose of 160 mg BID in combination with PDR001 400 mg every 4 weeks. After the initial 10 patients complete at least the first cycle of treatment, safety and available PK data will be analyzed to determine if an increase of the NIR178 dose to 240 mg BID is warranted, see [Section 4.1.3](#). For the Japanese safety run-in three dose levels of NIR178 will be evaluated (80mg,160mg and 240mg). As of protocol amendment 6, patients enrolled in the Japanese safety run-in will be administered NIR178 240mg hard gelatin capsules BID in combination with PDR001 400mg every 4 weeks starting at Cycle 1 Day 1.

A starting dose of NIR178 160 mg BID in combination with PDR001 using the new FCT formulation was selected based on the following considerations:

- NIR178 240 mg BID in combination with PDR001 400 mg QW4 was declared as MTD, based on clinical data with the existing formulation;
- FCT (administration as intact tablet) increased the bioavailability of NIR178 in dog relative to existing capsule formulation (administered as intact capsule) by 17% (refer to [Table 1-1](#));
- Decrease in variability of PK parameters of FCT (CV% of AUC_{last} decreased from 69 to 41 and CV% of C_{max} decreased from 69 to 34);
- Cumulative safety data of NIR178 at the dose 240 mg BID + PDR001 in other tumor indications (e.g., RCC, mCRPC) using existing capsule formulation is not yet available.

Preliminary evidence, based on emerging data from the current phase 2 study CNIR178X2201, shows that patients may derive more clinical benefit from a higher starting dose of NIR178, more specifically:

[figure not shown]

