4.1.3 Part 3: NIR178+PDR001 additional exploration in selected tumor types

Part 3 of the study will be an expansion of an intermittent or continuous NIR178 dosing schedule (if selected) and further evaluation of safety, efficacy, and immune modulation of the alternate NIR178 schedule in combination with PDR001 in one or two tumor groups of 20 patients each. If Part 3 is initiated, a total of 50 patients would be enrolled to this part. The one or two tumor groups in Part 3 will be selected based on the emerging data from Part 1 and Part 2. If one of the tumor groups selected for Part 3 is NSCLC, this group will enroll patients previously exposed to immunotherapy.

Novartis may decide to not open Part 3 for enrollment based on emerging data from Part 1 and Part 2.

As of Protocol Amendment 6, TNBC is one of the selected tumor groups and will enroll patients with a known PD-L1 SP142 status of IC=0 (<1%). Part 3 of the study will evaluate continuous BID NIR178 dosing schedule using the FCT NIR178 formulation. In specific, evaluation of safety, efficacy, and immune modulation of the continuous NIR178 schedule in combination with PDR001 will be performed in the TNBC tumor group which will consist of 20-30 patients. An additional tumor group may be considered for Part 3 which may enroll 20 patients.

Part 3 of the study will start with the FCT formulation of NIR178 at 160mg BID in combination with PDR001 400mg Q4W as a PK/safety run-in part. After the first 10 patients complete at least 1 cycle, a safety analysis will be conducted to decide whether to increase the NIR178 dose

to 240mg BID or complete Part 3 with NIR178 160mg BID. The dose increment criteria is as follows:

- If < 2 patients of the 10 evaluable patients have Grade 3/4 AEs suspected to be related study drug with 1 cycle of study treatment, dose escalate to 240 mg BID and enroll 20 additional patients
- If 2 or 3 patients of the 10 evaluable patients have Grade 3/4 AEs suspected to be related study drug with 1 cycle of study treatment, 10 more patients will be enrolled at 160 mg BID
- If > 3 patients of the 10 evaluable patients have Grade 3/4 AEs suspected to be related study drug with 1 cycle of study treatment, no additional patients will be enrolled and development of the FCT formulation will be reassessed.

Cumulative data (including safety, tolerability, preliminary anti-tumor activity, PK, and PD) will be reviewed on an ongoing basis by Novartis and study investigators via teleconferences.

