If initiated, 20 patients will be enrolled in each of the one or two tumor groups (max two) selected based on emerging data from Part 1 and Part 2. For the one or two tumor groups selected in Part 3, appropriate intervals will be defined and specified before any reporting activity in the statistical analysis plan. Novartis may decide to not open Part 3 for enrollment based on emerging data from Part 1 and Part 2.

As of protocol amendment 6, 20-30 patients will enroll in TNBC tumor group using NIR178 continuous dosing schedule in combination with PDR001. A second tumor group may be considered for Part 3 after completion of Part 1, see [Section 4.1.3](#).

A sample size of 10 patients treated at 160 mg BID FCT NIR178 in combination with PDR001 in TNBC tumor group in Part 3 provides a high probability, 77%, of observing 0 or 1 adverse event when the true incidence rate is 9%. ([Table 10-6](#)).

[figure not shown]
Table 10-6 Probability of detecting adverse events with specified incidence rate based on N=10 patients

Number of adverse events	AE incidence rate			
	0.05	0.09	0.12	0.15
0 or 1	0.91	0.77	0.66	0.54
2 or 3	0.09	0.22	0.32	0.41
>3	0.00	0.01	0.02	0.05

Regarding the efficacy of part 3, [Table 10-7](#) shows the posterior mean and corresponding 95% credible interval for N=20 for various observed ORR rates using a minimally informative unimodal beta prior distribution with parameters a=0.176 and b=1 for TNBC patients (Note: this assumes a priori response rate of 15%). From [Table 10-7](#), with a sample size of 20 patients, if the observed ORR rate is 15%, the probability of true ORR rate for TNBC patients to be at least 13% is 54.8%

Table 10-7 Posterior mean and 95% credible intervals for given ORR rates

ORR (N, %)	Posterior mean (95% credible interval)	Probability of no improvement [0% - 5%]	Probability of limited improvement (5%-13%)	Probability of clinically meaningful improvement [13%-100%]
0(0%)	0.008 (0.00,0.066)	0.958	0.038	0.004
2 (10%)	0.103 (0.015, 0.259)	0.220	0.495	0.285
3 (15%)	0.150 (0.036, 0.326)	0.060	0.392	0.548
4 (20%)	0.197 (0.062, 0.386)	0.012	0.217	0.771
5 (25%)	0.244 (0.091, 0.443)	0.002	0.092	0.906
10 (50%)	0.481 (0.277, 0.688)	0.000	0.000	1.000

Japanese safety run-in part

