Regarding the efficacy of part 3, [Table 3-5](#) shows the posterior mean and corresponding 95% credible interval for N=20 for various observed ORR rates using a minimally informative unimodal beta prior distribution with parameters $a=0.176$ and $b=1$ for TNBC patients (Note: this assumes a priori response rate of 15%). From [Table 3-5](#), with a sample size of 20 patients, if the observed ORR rate is 15%, the probability of true ORR rate for TNBC patients to be at least 13% is 54.8%

Table 3-5 Posterior mean and 95% credible intervals for given ORR rates

ORR (N, %)	Posterior mean (95% credible interval)	Probability of no improvement [0% - 5%]	Probability of limited improvement (5%-13%)	Probability of clinically meaningful improvement [13%-100%]
0(0%)	0.008 (0.00,0.066)	0.958	0.038	0.004
2 (10%)	0.103 (0.015, 0.259)	0.220	0.495	0.285
3 (15%)	0.150 (0.036, 0.326)	0.060	0.392	0.548
4 (20%)	0.197 (0.062, 0.386)	0.012	0.217	0.771
5 (25%)	0.244 (0.091, 0.443)	0.002	0.092	0.906
10 (50%)	0.481 (0.277, 0.688)	0.000	0.000	1.000

Japanese safety run-in part

The period for evaluating DLTs will be cycle 1 (i.e. the first 28 days of treatment with single agent NIR178 or in combination with PDR001). The safety run-in will evaluate three NIR178 dose levels sequentially. Each dose level may consist of 3 to 6 newly enrolled patients who have tumor histologies specified in Protocol Section 5, and who meet all other inclusion/exclusion criteria. The dose escalation strategy is detailed in [Section 1.1.4](#).

4 Change to protocol specified analyses

The study is closed out due to lack of sufficient efficacy and there is only TNBC indication opened in Part 3 at a single dose level - NIR178 160 mg BID. The dose increment criteria of Part 3 described in Section 1.1.3 will not be evaluated as no patients are enrolled at 240mg in Part 3.

5 Appendix

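### Protocol Section 6.1.1 has no stop branch for the Part 3 tablet dose decision, so it contradicts Section 4.1.3 when more than 3 of 10 patients have related Grade 3/4 AEs

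*Protocol*

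**What the plan says.** **Protocol 4.1.3, repeated in SAP 1.1.3.** Part 3 starts at 160 mg BID FCT. After the first 10 patients complete at least one cycle, the number with study-drug-related Grade 3/4 AEs in that cycle sets the next step. Fewer than 2: escalate to 240 mg and enrol 20. Two or 3: enrol 10 more at 160 mg. More than 3: "no additional patients will be enrolled and development of the FCT formulation will be reassessed".

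**Protocol 6.1.1, the dosing section.** The same decision has two outcomes and no count. "If there is unexpected toxicity due to formulation change", then "the dose will not be escalated to NIR178 240mg BID FCT and an additional 10 patients will be enrolled at NIR178 160mg BID FCT". Otherwise, "If the NIR178 160mg BID FCT formulation is considered safe, dose escalation to NIR178 240 mg BID FCT will occur", with 20 more patients. Section 4.1.3 is not cited.

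**Protocol 2.3.** This also summarises the decision ("safety and available PK data will be analyzed to determine if an increase of the NIR178 dose to 240 mg BID is warranted"), but it sends the reader to Section 4.1.3.

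**Protocol 10.8.** Table 10-6 ("Probability of detecting adverse events with specified incidence rate based on N=10 patients") gives the probability of each branch of the counted gate.

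**SAP Section 4.** The dose increment criteria "described in Section 1.1.3 will not be evaluated as no patients are enrolled at 240mg in Part 3". The sentence before it says that the study was closed for lack of sufficient efficacy.

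**The concern.** The stop branch protects later patients if the tablet proves more toxic than planned. Section 6.1.1 is where a reader looks for dosing rules. Its toxicity trigger, harm attributed to the new formulation, describes the situation that the stop exists for, yet its answer is to keep enrolling at the same dose. Anyone following it literally would continue where Section 4.1.3 halts. Part 3 has no independent monitoring committee (Protocol 8.6), so the written rule carries more of the load.

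The stop concerns further enrolment only. Neither section uses it to take the first ten patients off the tablet.

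A smaller, separate point concerns SAP Section 4. The gate is counted on patients at 160 mg. The absence of anyone at 240 mg could follow from the middle branch, from the stop branch or from closing the study, so it is not a reason why the gate cannot be evaluated.

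**Working it through.** **Step 1. Set the rules side by side.**

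| Patients of the first 10 with related Grade 3/4 AEs | Protocol 4.1.3 and SAP 1.1.3 | Protocol 6.1.1 as worded |
|---|---|---|
| 0 or 1 | Escalate, 20 more | Same, if judged safe |
| 2 or 3 | 10 more at 160 mg | Same, if judged unexpected and due to the tablet; otherwise not determined |
| More than 3 | 0 more, reassess tablet | 10 more at 160 mg |

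The 6.1.1 trigger is a judgement about cause and the 4.1.3 trigger is a count, so the first two rows match only loosely. The last row does not depend on how the trigger is read: neither outcome in 6.1.1 is zero further patients.

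**Step 2. Reproduce Table 10-6.** Let X be the number of the 10 patients with a related Grade 3/4 AE, X ~ Binomial(10, p), with P(X = k) = C(10,k) p^k (1−p)^(10−k). At p = 0.09, P(X ≤ 1) = 0.91^10 + 10 × 0.09 × 0.91^9 = 0.3894 + 0.3851 ≈ 0.775. The plan states 77%. All 12 cells of the table reproduce.

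**Step 3. Size of the contradictory branch.** P(X > 3) = 1 − P(X ≤ 3). Its share of all non-escalation outcomes is P(X > 3) / P(X ≥ 2). If 6.1.1 were followed literally, the expected extra patients, not conditional on reaching that branch, are 10 × P(X > 3). The expected extra patients with a related Grade 3/4 AE are 10 × p × P(X > 3).

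| True rate p | P(0–1) | P(2–3) | P(>3) | Share of non-escalation | Extra patients | Extra cases |
|---|---|---|---|---|---|---|
| 5% | 0.914 | 0.085 | 0.0010 | 1.2% | 0.01 | 0.0005 |
| 9% | 0.775 | 0.217 | 0.0088 | 3.9% | 0.09 | 0.008 |
| 12% | 0.658 | 0.318 | 0.0239 | 7.0% | 0.24 | 0.029 |
| 15% | 0.544 | 0.406 | 0.0500 | 11.0% | 0.50 | 0.075 |
| 20% (assumed) | 0.376 | 0.503 | 0.1209 | 19.4% | 1.21 | 0.242 |

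The 20% row is an assumption. The nearest figure in the documents is Protocol 1.2.1.4: among the first 10 patients on 240 mg capsules, "G3 AEs suspected to be related to study drug occurring in two patients". That is a different dose and formulation, and the events are not said to be limited to cycle 1. The row shows only how the branch grows if the tablet is more toxic than planned.

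**The case against.** The best defence is that 6.1.1 is shorthand and not a rival rule. The counted gate is explicit in Protocol 4.1.3 and repeated in SAP 1.1.3, and Protocol 2.3 and 10.8 both point to 4.1.3. Section 4.1.3 itself uses a two-way summary (increase the dose or complete at 160 mg) just before listing the three branches. The Figure 4-1 and Table 6-5 footnotes do the same. A site could not act on its own reading either: the decision follows a study-level safety analysis with sponsor and investigator review, treatment allocation runs through IRT, and the sponsor can terminate for safety at any time.

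Most of this stands. It makes 4.1.3 the evident controlling rule and keeps the expected harm small. It does not make 6.1.1 correct. In 4.1.3 the two-way summary sits beside the stop, whereas in 6.1.1 nothing supplies it, and 6.1.1 goes beyond summary by prescribing 10 more patients.

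A reader might infer that the protocol runs two competing dose rules throughout, or that the two texts agree exactly everywhere except above 3 of 10. Neither is supported, because a judgement about formulation toxicity cannot be mapped one-to-one onto counts. A reader might also infer from SAP Section 4 that a stop was met and passed over. The documents do not say whether ten patients reached the gate or what the count was, and closure for lack of efficacy is an ordinary explanation.

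**Conclusion.** The inconsistency is real and minor. It is a clear contradiction in one branch, more than 3 of 10, where Section 4.1.3 enrols no one further and 6.1.1 as worded enrols 10. Over the Table 10-6 rates of 5% to 15%, that branch has probability 0.1% to 5.0%. Literal use of 6.1.1 would then add 0.01 to 0.5 expected patients and at most 0.075 expected related Grade 3/4 cases. These figures assume independent patients with a common AE rate, the same rate in the next ten, and a team that works from 6.1.1 and not from 4.1.3. Nothing in the documents suggests that any team did so.

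The efficacy analysis is unaffected, and closure of the study limits the practical weight further. The SAP Section 4 remark is secondary: the stated reason does not follow for a gate counted at 160 mg, but this changes no planned analysis.

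**What to change.** In Protocol 6.1.1, replace the two-outcome text with a reference to the Section 4.1.3 criteria, naming the stop to further enrolment when more than 3 of 10 patients have related Grade 3/4 AEs. Section 2.3 already refers to 4.1.3 in this way.

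Optionally, reword SAP Section 4 so that non-evaluation of the gate rests on its actual cause, for example study closure, and not on the absence of 240 mg patients. Any observed count and branch are results and belong in the clinical study report, not in a plan finalised before database lock.

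The cost is one sentence in each document and no new data. Cut-offs, doses and the definition of who is evaluable stay as they are.
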